5.4 Safety Set

The Safety Set consists of all randomly assigned participants who receive the IP. The Safety Set will be used for all analyses of safety, except for the solicited ARs. Participants will be included in the vaccination group corresponding to what they actually received according to the following rules:

- mRNA-1030 CCI group: If the received dose of mRNA-1030 is CCI [REDACTED]
[REDACTED]
- mRNA-1030 CCI group: If the received dose of mRNA-1030 is CCI [REDACTED]
[REDACTED]
- mRNA-1030 CCI group: If the received dose of mRNA-1030 is CCI [REDACTED]
- mRNA-1020 CCI group: If the received dose of mRNA-1020 is CCI [REDACTED]
[REDACTED]
- mRNA-1020 CCI group: If the received dose of mRNA-1020 is CCI [REDACTED]
[REDACTED]
- mRNA-1020 CCI group: If the received dose of mRNA-1020 is CCI [REDACTED]
[REDACTED]
- mRNA-1020 (HA only comparator) group: If the received dose of mRNA-1020/mRNA-1030/Flublok is 0 μ g and mRNA-1010 >0 μ g
- Flublok (active comparator) group: If the received dose of mRNA-1020/mRNA-1030/mRNA-1010 is 0 μ g and Flublok >0 μ g

5.5 Solicited Safety Set

The Solicited Safety Set consists of all participants in the Safety Set who contribute any solicited AR data. The Solicited Safety Set will be used for the analyses of solicited ARs and participants will be included in the vaccination group corresponding to what they actually received as shown in [Section 5.4](#).

6 STATISTICAL ANALYSIS

6.1 Planned Analyses

6.1.1 Interim Analysis (IA)

An interim analysis will be performed after participants have completed the Day 29 Visit. All data relevant to the IA through the Day 29 Visit will be cleaned (i.e., data that are as clean as possible).

The IA will be performed by a separate team of unblinded statisticians and programmers. Except for a limited number of Sponsor and CRO personnel who will be unblinded to perform the IA, the study site staffs, Investigators, study monitors, and participants will remain blinded until after the final database lock for final analysis.

6.1.2 Internal Safety Team (IST) Review

A blinded IST will comprise Sponsor physicians. The IST will conduct a scheduled review of safety data after approximately 96 participants (approximately 12 per study arm) have completed the Day 8 visit as well as ad hoc safety data review if requested by the study medical monitor and the study team.

6.1.3 Data Safety Monitoring Board (DSMB) Review

The DSMB, composed of external/independent participant matter experts, will conduct unblinded reviews of safety data on an ad hoc basis if any pause rule is met or as otherwise requested by the study team and/or IST. The DSMB will review unblinded IA results and make recommendations to sponsor.

6.1.4 Final Analysis

The final analysis of safety, reactogenicity, and immunogenicity will be performed after all participants have completed all planned study procedures. The results of this analysis will be presented in a final clinical study report, including individual listings.

6.2 General Considerations

The Schedules of Events (SoE) are provided in Table 1 of the protocol Section 1.3.

General considerations for analyses will be applied to this study, unless otherwise specified. All analyses will be performed by treatment arm, unless otherwise specified. Statistical outputs (tables, figures, listings, and datasets) will refer to study participants as participants and will use vaccination, injection of IP and injection interchangeably. All

analyses will be conducted using SAS Version 9.4. All table data will have a corresponding listing.

6.2.1 Data Precision

For the summary statistics of all numerical variables unless otherwise specified, the display precision will follow programming standards. Please see [Appendix A](#) for variable display standards.

When count data are presented, the percentage will be suppressed when the count is zero in order to draw attention to the non-zero counts. A row denoted “Missing” will be included in count tabulations where specified on the shells to account for dropouts and missing values. The denominator for all percentages will be the number of participants in that vaccination group within the analysis set of interest, unless otherwise specified.

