For the immunogenicity endpoints, geometric mean of specific antibody titers with corresponding 95% CI at each time point and geometric mean fold rise (GMFR) of specific antibody titers with corresponding 95% CI at each postbaseline time point over preinjection baseline at Day 1 will be provided by vaccination group. Descriptive summary statistics including median, minimum, and maximum will also be provided. Geometric mean titer (GMT) and GMFR might be adjusted for baseline titer and/or age group.

For summarizations of geometric mean titers, antibody titers reported as below lower limit of quantification (LLOQ) will be replaced by $0.5 \times LLOQ$. Values that are greater than the upper limit of quantification (ULOQ) will be converted to the ULOQ.

For HA, rate of seroconversion is defined as the proportion of participants with either a pre-vaccination HI titer < 1:10 and a postvaccination HI titer ≥ 1:40 or a prevaccination HI titer $\geq 1:10$ and a minimum 4-fold rise in postvaccination HI antibody titer. For NA, an endpoint of interest is the percentage of participants with a change in the Day 29 titer of at least 2-/3-/4-

fold rise, defined as $\geq 2-/3-/4$ -fold of the LLOQ if the Day 1 titer is < LLOQ; or $\geq 2-/3-/4$ -fold of the Day 1 titer if the Day 1 titer is \geq LLOQ.

Seroconversion rate from baseline will be provided with a 2-sided 95% CI using the Clopper-Pearson method at each postbaseline time point. For NA, the number and percentage of participants with $a \ge 2$ -, ≥ 3 -, and ≥ 4 -fold rise of serum titers from baseline will be provided with 2-sided 95% CI using the Clopper-Pearson method at each postbaseline time point.

Further details will be described in the SAP.

9.5.4. **Exploratory Analyses**

Exploratory analyses not addressed in Section 9.5.1 and Section 9.5.3 will be described in the SAP before database lock.

9.5.5. **Subgroup Analyses**

The protocol does not define any formal subgroup analyses. However, age-specific subgroup analyses may be performed to assess for potential differences in safety/reactogenicity or immune responses across age groups.

9.6. **Study Analyses**

One unblinded IA is planned in this study. It will be performed after participants have completed the Day 29 Visit and will include, at a minimum, cleaned data (ie, data that are as clean as possible) from available safety and immunogenicity datasets.

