5.3 Per-Protocol (PP) Set

The PP Set consists of all participants in the FAS who comply with the injection schedule, comply with the timings of immunogenicity blood sampling to have a baseline and at least 1 post-injection assessment, do not have influenza infection at baseline through Day 29 (as documented by PCR testing), and have no major protocol deviations that impact the immune response. The PP Set will be used as the primary analysis set for analyses of immunogenicity unless otherwise specified. Participants will be analyzed according to the vaccination group to which they were randomized.

Participants compliant with the timing of immunogenicity blood sampling are required to have a baseline assessment, at least one post-injection assessment, and a Day 29 assessment that is within 21 days to 42 days after injection (-7 / +14 days of Day 29).

Participants with a dosing error will be considered as having a protocol deviation. However, the determination of whether to include/exclude participants from the PP Set due to a dosing error will be based on the dosage difference (in μ g) between the actual dose received and the randomized dose. The PP Set exclusion criteria for participants with dosing error are described in [Table 2](#). For the mRNA-1020 and the mRNA-1030 arms, acceptable dosing deviation from the randomized dose is up to **CCI** [REDACTED]. For the mRNA-1010 active comparator, participants who are randomized to the active comparator arm but received less than **CCI** [REDACTED] of the active comparator or any amount of mRNA-1020, mRNA-1030, or Flublok active comparator will be excluded from the PP Set. For the Flublok active comparator, participants who are randomized to the active comparator arm but received less than **CCI** [REDACTED] of the active comparator or any amount of mRNA-1020, mRNA-1030, or mRNA-1010 active comparator will be excluded from the PP Set.

Table 2 PP Set Exclusion Criteria for Dosing Errors

	Randomized Dose							
	mRNA-1020	mRNA-1030			mRNA-1010 (active comparator) ¹		Flublok (active comparator) ²	
Actual Dose Received	CCI							
mRNA-1020								
	CCI	Y	Y	Y	Y	Y	Y	Y
	CCI	Y	Y	Y	Y	Y	Y	Y
	CCI	Y	Y	Y	Y	Y	Y	Y
	CCI	Y	Y	Y	Y	Y	Y	Y
	CCI	Y	Y	Y	Y	Y	Y	Y
	CCI	Y	Y	Y	Y	Y	Y	Y
	CCI	Y	Y	Y	Y	Y	Y	Y
	CCI	Y	Y	Y	Y	Y	Y	Y
	CCI	Y	Y	Y	Y	Y	Y	Y
	CCI	Y	Y	Y	Y	Y	Y	Y
	CCI	Y	Y	Y	Y	Y	Y	Y
	CCI	Y	Y	Y	Y	Y	Y	Y
	CCI	Y	Y	Y	Y	Y	Y	Y
	CCI	Y	Y	Y	Y	Y	Y	Y
	CCI	Y	Y	Y	Y	Y	Y	Y
	CCI	Y	Y	Y	Y	Y	Y	Y
	CCI	Y	Y	Y	Y	Y	Y	Y
	CCI	Y	Y	Y	Y	Y	Y	Y
	CCI	Y	Y	Y	Y	Y	Y	Y

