6.2.5 Handling Non-Quantifiable Antibody Values

For calculation regarding antibody levels/titers, antibody values reported as below lower limit of quantification (LLOQ) will be replaced by $0.5 \times \text{LLOQ}$. Values that are greater than the upper limit of quantification (ULOQ) will be converted to the ULOQ. Missing results will not be imputed.

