6.2.8 Handling Missing and Incomplete Data

- Imputation rules for missing dates of prior/concomitant medications, non-study vaccinations and procedures are provided in [Appendix C](#).
- Imputation rules for missing AE dates are provided in [Appendix D](#).
- For laboratory assessments, if majority of results are indefinite, imputation of these values will be considered. If the laboratory results are reported as below the LLOQ (e.g., < 0.1), the numeric values will be replaced by $0.5 \times \text{LLOQ}$ in the summary. If the laboratory results are reported as greater than the ULOQ (e.g., > 3000), the numeric values will be replaced by ULOQ in the summary.
- Other incomplete/missing data will not be imputed, unless otherwise specified.

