6.5 Immunogenicity Analysis

The analyses of immunogenicity will be based on the PP Set and will be performed by vaccination group and by age group.

If the number of participants in the FAS and PP Set differs (defined as the difference divided by the total number of participants in the PP Set) by more than 10% for each age

group, supportive analyses of immunogenicity may be conducted using the FAS. The supportive analysis is required if the condition is met.

The GMT and geometric mean (GM) level will be calculated using the following formula:

$$2^{\left\{ \frac{\sum_{i=1}^n \log_2(t_i)}{n} \right\}}$$

where t_1, t_2, \dots, t_n are n observed immunogenicity titers or levels.

The GMFR measures the changes in immunogenicity titers or levels within participants. The GMFR will be calculated using the following formula:

$$2^{\left\{ \frac{\sum_{i=1}^n \log_2(v_{ij}/v_{ik})}{n} \right\}} = 2^{\left\{ \frac{\sum_{i=1}^n \log_2(v_{ij}) - \log_2(v_{ik})}{n} \right\}}$$

where, for n participants, v_{ij} and v_{ik} are observed immunogenicity titers or levels for participant i at time points j and $k, j \neq k$.

The 95% CIs for GMT and GMFR will be calculated based on the t distribution of the log-transformed values then back transformed to the original scale for presentation, unless otherwise specified. Reverse cumulative distribution plot will be generated.

The model-based GM titer will be estimated based on an analysis of covariance (ANCOVA) model. In the ANCOVA model, the log-transformed antibody titer at a post baseline timepoint (Day 29) are treated as a dependent variable, with the treatment group as an explanatory variable and the log-transformed baseline antibody titer as a covariate, adjusting for the stratification factor(s) as appropriate, that is, age groups (18 to 49 years old, and 50 to 75 years old of age).

The GMT will be estimated by the geometric least square mean (GLSM) from the ANCOVA model for each treatment group and corresponding 95% CI will be provided.

For each pair of between-group comparison specified in [Table 3](#), the GMR (ratio of GMTs) between the two treatment groups in each pair will be estimated from the ANCOVA model, with 95% CI provided accordingly.

For each pair of between-group comparison specified in [Table 3](#), the difference of seroconversion rate (SCR) between the two treatment groups in each pair at Day 29 will be provided, with 95% CI estimated using Miettinen-Nurminen method.

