6.5.3 Secondary Analysis of Immunogenicity

For each vaccination group, the following evaluations will be performed at all evaluable humoral immunogenicity time points.

GMTs and GMFRs:

- GMT of vaccine-matched strain-specific anti-HA antibodies with corresponding 95% CI will be provided at each time point,. Geometric mean (GM) level and corresponding 95% CI will be plotted at each time point.
- GMT of vaccine-matched strain-specific anti-NA antibodies with corresponding 95% CI will be provided at each time point.GM level and corresponding 95% CI will be plotted at each time point.
- GMFR of vaccine-matched strain-specific anti-HA antibodies with corresponding 95% CI will be provided at each post-baseline time point over pre-injection baseline at Day 1. GMFR and corresponding 95% CI will be plotted at each time point.
- GMFR of vaccine-matched strain-specific anti-NA antibodies with corresponding 95% CI will be provided at each post-baseline time point over pre-injection

baseline at Day 1. GMFR and corresponding 95% CI will be plotted at each time point.

- In addition, the following descriptive statistics will also be provided at each time point: the number of participants (n), median, minimum, and maximum.
- Reverse cumulative distribution function curve at each time point will be provided.
- Listing of anti-HA antibodies for vaccine-matched seasonal influenza A and B strains will be provided based on the PP Set.
- Listing of anti-HA antibodies for vaccine-matched seasonal influenza A and B strains for participants with influenza infection will be provided based on the PP Set.
- Listing of anti-NA antibodies for vaccine-matched seasonal influenza A and B strains will be provided based on the PP Set.
- Listing of anti-NA antibodies for vaccine-matched seasonal influenza A and B strains for participants with influenza infection will be provided based on the PP Set.

Seroconversion:

For each vaccination group, the following evaluations will be performed at each post-baseline time point.

- For HA, the number and percentage of participants with seroconversion at each post-baseline time point will be provided with 2-sided 95% CI using the Clopper-Pearson method.

2-/3-/4-fold Rise:

For NA: For each vaccination group, the following evaluations will be performed at each post-baseline time point.

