- The number and percentage of participants with a \geq 2-fold rise at each post-baseline time point in anti-NA antibody titers from baseline will be provided with 2-sided 95% CI using the Clopper-Pearson method.

- The number and percentage of participants with a ≥ 3 -fold rise at each post-baseline time point in anti-NA antibody titers from baseline will be provided with 2-sided 95% CI using the Clopper-Pearson method.
- The number and percentage of participants with a ≥ 4 -fold rise at each post-baseline time point in anti-NA antibody titers from baseline will be provided with 2-sided 95% CI using the Clopper-Pearson method.

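### Under the SAP's default denominator, the descriptive Day 8 and Day 181 seroconversion and NAI fold-rise rates would be diluted by participants who have no titer at that visit

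*SAP*

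**What the plan says.** SAP 6.2.1 (Data Precision) gives the general rule for percentages: "The denominator for all percentages will be the number of participants in that vaccination group within the analysis set of interest, unless otherwise specified." The sentence before it allows a row for missing values in count tables, but only where the shells call for one.

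SAP 6.5.3 asks for response rates at every visit after baseline. For HAI: "For HA, the number and percentage of participants with seroconversion at each post-baseline time point will be provided", with a Clopper-Pearson interval. For NAI, the number and percentage with a 2-, 3- or 4-fold "rise at each post-baseline time point in anti-NA antibody titers from baseline will be provided", again with Clopper-Pearson intervals. Protocol 9.5.3 has the same plan: "Seroconversion rate from baseline will be provided with a 2-sided 95% CI". None of these sections names a denominator. SAP 6.4.1, by contrast, restates the base for unsolicited adverse events (the Safety Set within each vaccination group).

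The rates are computed in the Per-Protocol Set. Under SAP 5.3, participants compliant with blood sampling "are required to have a baseline assessment, at least one post-injection assessment, and a Day 29 assessment" within 21 to 42 days after injection. No Day 8 or Day 181 sample is required. Protocol 7.3 says that participants who withdraw are not replaced.

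GMT and GMFR are defined in SAP 6.5 over n "observed immunogenicity titers or levels". On absent values, SAP 6.2.5 says "Missing results will not be imputed" and SAP 6.2.8 says "Other incomplete/missing data will not be imputed, unless otherwise specified".

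**The concern.** A participant who gives a Day 29 sample and then leaves the study stays in the Per-Protocol Set with no Day 181 titer. Under the 6.2.1 default, that person is in the denominator and cannot be in the numerator, so has the same effect on the rate as a non-responder. The GMT and GMFR for the same visit leave the person out, so the two summaries would rest on different numbers.

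Two misreadings could follow. Dropout accumulates, so a Day 181 rate could fall below the Day 29 rate with no change among those tested and look like waning. Vaccination groups with unequal dropout could also look different in persistence when they are not. Separately, a programmer who gives more weight to the no-imputation rules could reasonably divide by participants with titers, so the same data could yield two different published rates.

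**Working it through.** **The plan's own figures.** The documents give no missing-titer rate, no expected response rate and no worked denominator. The only sample-size figures are the chances of seeing at least one adverse event among 70 (SAP 4.3). They reproduce: 1 − 0.98^70 = 75.7% (stated as about 76%) and 1 − 0.96^70 = 94.3% (stated as about 94%). They supply only the group size used below.

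**Inputs.** N = 70 per vaccination group (SAP 4.3), taken as the Per-Protocol size for illustration. Response among those with a titer, about 60%: assumed. Number without a titer: assumed and varied.

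**Formula.** Let x be the number of responders, n the number with a titer, and m = (N − n)/N the share without one. The rate among those tested is r = x/n. The rate under the default is x/N = r × (1 − m). The relative fall is exactly m and the absolute fall is r × m.

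**Results for N = 70.**

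| Visit | Without titer | m | Among those with a titer | Under 6.2.1 default |
|---|---|---|---|---|
| Day 8 | 2 | 2.9% | 41/68 = 60.3% | 41/70 = 58.6% |
| Day 181 | 4 | 5.7% | 40/66 = 60.6% | 40/70 = 57.1% |
| Day 181 | 7 | 10.0% | 38/63 = 60.3% (47.2 to 72.4) | 38/70 = 54.3% (41.9 to 66.3) |
| Day 181 | 10 | 14.3% | 36/60 = 60.0% | 36/70 = 51.4% |

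Intervals are Clopper-Pearson 95%.

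**Range over other response rates.** With 4 missing, the fall runs from 20/66 − 20/70 = 30.3% − 28.6% = 1.7 points to 46/66 − 46/70 = 69.7% − 65.7% = 4.0 points. With 14 missing, it runs from 17/56 − 17/70 = 30.4% − 24.3% = 6.1 points to 39/56 − 39/70 = 69.6% − 55.7% = 13.9 points.

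**Apparent waning.** Day 29 with all 70 tested: 42/70 = 60.0%. Day 181 with 7 missing, under the default: 54.3%. The fall is 60.0 − 54.3 = 5.7 points, although 60.3% of those tested still respond.

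**Apparent difference between groups.** Groups with 4 and 10 missing at Day 181 would show 57.1% and 51.4%, a gap of 5.7 points. Among those tested the rates are 60.6% and 60.0%, a gap of 0.6 points.

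**Day 29.** In the Per-Protocol Set a Day 29 assessment is required, so m is close to 0 and the two bases agree, except where a sample has no result for one strain or assay. The between-group seroconversion differences in SAP 6.5 are at Day 29 only. The Full Analysis Set requires no titer, so its Day 29 rates would be exposed, but only if the supportive analysis is triggered (the sets differ by more than 10% of the Per-Protocol number, assessed by age group).

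**The case against.** The case for leaving the text alone has several parts.

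- **No listed endpoint or comparison depends on these rates.** SAP 3.1 lists seroconversion and fold rise at Day 29 only, SAP 3.2 lists GMT and GMFR only, and no hypothesis is tested. This stands and limits the point to a minor one.
- **The shells may already deal with it.** They are not in the documents and could show a missing row or use another base. This stands as a limit on what can be claimed. A missing row by itself would not change the denominator that 6.2.1 sets.
- **Readers would see the mismatch.** SAP 6.5.3 displays the number of participants at each time point beside the titer summaries, together with reverse cumulative distribution curves. This reduces the risk of misreading but does not correct the percentage or its interval.
- **Few titers may be missing.** Protocol 7.3 has the investigator ask withdrawing participants to complete pending procedures. Appendix B of the SAP accepts unscheduled samples in wide windows (study days 2 to 18 for Day 8, 106 onward for Day 181). Only a truly absent titer counts, so the effect may be small.
- **The shift is small beside sampling error.** For 57.1% against 51.4% with 70 per group, the Wald half-width for the difference is 1.96 × √(0.571 × 0.429/70 + 0.514 × 0.486/70) ≈ 16.5 points. That is true, but the dilution always goes in one direction, and wide intervals do not remove it.
- **The no-imputation rules might prevent it.** They say that no value is filled in, but they do not say who is in the denominator. They make the observed-titer base a reasonable reading without specifying it.

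A reader might also infer that an age-group rate would be divided by the whole vaccination group, because 6.2.1 names only the vaccination group. SAP 6.2.9 and 6.5 call for displays by vaccination group and by age group, with the appropriate population, so that is not a plausible reading.

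**Conclusion.** The point holds as a minor correction. A stated rule covers these percentages, nothing in SAP 6.5 to 6.5.3 overrides it, and applied literally it scales the Day 8 and Day 181 rates down by the share without a titer. With an assumed 7 of 70 missing at Day 181, the reported rate is about 6 points too low as a description of those tested (60.3% against 54.3%). With 2 of 70 missing at Day 8 it is under 2 points. All missing counts and response rates here are assumptions.

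Two stronger conclusions might be inferred. One is that the primary immunogenicity results are biased. They are not: the required Day 29 sample protects the Per-Protocol rates and differences. The other is that the study tables will show diluted rates. The documents cannot establish that without the shells. What they do establish is that the written rule, taken alone, gives the diluted figure.

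**What to change.** Add one sentence to SAP 6.5, to apply to 6.5.2 and 6.5.3: *Seroconversion and 2-/3-/4-fold-rise percentages and CIs use participants in the analysis set and displayed subgroup with a non-missing baseline titer and a non-missing titer for that strain, assay and time point (N1, displayed).* Add an N1 line to the shells. If the shells already work this way, the sentence records it in the SAP. It also settles the base for age-group displays and for any supportive Full Analysis Set analysis.

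The cost is small. Intervals are slightly wider when titers are missing: with 7 of 70 missing, 25.2 points on the base of 63 against 24.3 points on the base of 70 (widths from unrounded limits). The rate among those with a titer assumes that missingness is unrelated to response, and the displayed N1 lets readers judge how much depends on that.
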